This document cannot be used to support any marketing authorization application and any extensions or variations thereof.

REDACTED COPY

LIST OF ABBREVIATIONS

AE	adverse event
AED	antiepileptic drug
ALP	alkaline phosphatase
ALT	alanine aminotransferase
AST	aspartate aminotransferase
bid	twice daily
BP	blood pressure
BRV	brivaracetam
CDMS	clinical data management system
CRF	Case Report form
CRO	contract research organization
C-SSRS	Columbia-Suicide Severity Rating Scale
DMC	Data Monitoring Committee
ECG	electrocardiogram
GCP	Good Clinical Practice
HLA	human leukocyte antigen
ICF	Informed Consent Form
ICH	International Council for Harmonisation
IEC	Independent Ethics Committee
IIB	Initiating iv BRV
IMP	investigational medicinal product
IOB	Initiating Oral BRV
IRB	Institutional Review Board
IRT	interactive response technology
iv	intravenous
MedDRA [®]	Medical Dictionary for Regulatory Activities [®]
OLB	Open-label BRV
PCS	possibly clinically significant
PD	pharmacodynamic(s)
PDILI	potential drug-induced liver injury
PK	pharmacokinetic(s)

PK-PPS	PK Per-protocol Set
POS	partial-onset seizures
PS	Patient Safety
q12h ±2h	every 12 hours ±2 hours
RR	respiratory rate
RxB	Prescribed-BRV
SAE	serious adverse event
SD	standard deviation
SOP	standard operating procedure
SS	Safety Set
SS-iv	Safety Set-iv
SV2A	synaptic vesicle protein 2A
TC	Telephone Contact
ULN	upper limit of normal
VNS	vagus nerve stimulation

REDACTED COPY
This document cannot be used to support any marketing authorization application and any extensions or variations thereof.

1 SUMMARY

EP0065 is a Phase 2, multicenter, open-label study with a primary objective of evaluating the pharmacokinetics (PK), safety, and tolerability of brivaracetam (BRV) administered as a 15-minute intravenous (iv) infusion and an iv bolus (up to 2-minute infusion) in subjects ≥ 1 month to < 16 years of age with epilepsy.

The following subjects will be eligible for enrollment in EP0065:

- Open-label BRV (OLB) subjects: currently receiving oral BRV as participants in a long-term, open-label study
- Prescribed-BRV (RxB) subjects: currently receiving prescribed oral BRV from commercial supply
- Initiating Oral BRV (IOB) subjects: not currently receiving BRV; first dose of BRV in EP0065 will be oral tablet or solution
- Initiating iv BRV (IIB) subjects: not currently receiving BRV; first dose of BRV in EP0065 will be administered intravenously

EP0065 includes the following consecutive periods:

Subjects	Screening Period 1 to 10 days	IOB Treatment Period 2 to 10 days	iv PK Period 1 to 6 days
OLB	Oral BRV	Not applicable	iv BRV
RxB	Oral BRV	Not applicable	iv BRV
IOB	No BRV	Oral BRV	iv BRV
IIB	No BRV	Not applicable	iv BRV

BRV=brivaracetam; IIB=Initiating iv BRV; IOB=Initiating Oral BRV; iv=intravenous;
OLB=Open-label BRV; PK=pharmacokinetic RxB=Prescribed-BRV

Note: Oral BRV will be administered as tablets or oral solution. Tablets will be administered orally, and oral solution will be administered either orally or by enteric administration (eg, feeding tube) based on subject need.

During the Screening Period, OLB and RxB subjects will continue to receive oral BRV (tablet or oral solution) in accordance with their long-term, open-label study dosing or prescribed dosing, respectively. The IOB and IIB subjects will not receive BRV during the Screening Period.

Eligible OLB, RxB, and IIB subjects will progress directly from the Screening Period to the iv PK Period, whereas IOB subjects will enter a 2- to 10-day IOB Treatment Period in which they receive oral BRV before progressing to the iv PK Period. The initial oral BRV dose in the IOB Treatment Period is 2mg/kg/day.

During the iv PK Period, iv BRV will be administered every 12 hours ± 2 hours (q12h ± 2 h). All subjects will receive 1 to 2 consecutive doses of BRV; however, based on medical need, subjects may receive up to 10 consecutive doses of iv BRV. Blood sampling for PK analyses (herein referred to as "PK sampling") will occur with the first iv BRV administration and with 1 other iv BRV administration. For OLB, RxB, and IOB subjects, the first iv BRV dose will be equivalent

(mg-to-mg) to the final dose of oral BRV prior to the first iv dose. For IIB subjects, the first iv BRV dose will be 1mg/kg, not to exceed 50mg for subjects with body weights ≥ 50 kg. For all subjects, iv BRV doses may be adjusted at the Investigator's discretion after PK sampling for 2 iv doses; however, no doses may exceed the maximum doses indicated below. During the iv PK Period, BRV may only be administered by iv infusion.

At the completion of the iv PK Period, subjects who will continue oral BRV treatment should enroll in a long-term, open-label BRV study. Subjects who have received ≥ 4 doses of BRV and do not plan to continue treatment with BRV after completion of the iv PK Period or who discontinue BRV treatment during the study will have a Down-Titration Period of up to 4 weeks (28 days) for gradual discontinuation of BRV and a Safety (BRV-free) Period of 2 weeks (14 days) after the final dose of BRV. Subjects who have received < 4 doses of BRV may have BRV down titrated at the discretion of the Investigator.

For IOB and IIB subjects, the maximum BRV dose is 4mg/kg/day (2mg/kg twice daily [bid]). For OLB and RxB subjects, the maximum BRV dose is 5mg/kg/day (rounded) in recognition of the possibility that some of these subjects may be using this dose when they enter EP0065.

Throughout the study, no subjects may receive a dose greater than BRV 200mg/day. Oral BRV will be administered in equally divided doses bid.

It is planned for approximately 50 enrolled subjects to receive iv BRV in the following age-based cohorts (approximately 12 subjects/cohort), with approximately half of the subjects in each cohort receiving iv BRV as a 15-minute (± 3 minutes) infusion and half receiving iv BRV as a bolus (up to 2-minute infusion).

- Cohort 1: ≥ 12 to < 16 years
- Cohort 2: ≥ 6 years to < 12 years
- Cohort 3: ≥ 2 to < 6 years
- Cohort 4: 1 month to < 2 years

Enrollment will be sequential by descending age beginning with Cohort 1. For each cohort, the first half will receive the 15-minute infusion. The Data Monitoring Committee (DMC) will then meet to review safety and PK data, as available. After the DMC safety review, the remaining half in that cohort will receive iv BRV as a bolus (up to 2-minute infusion), and the next cohort may begin the 15-minute infusion. Subjects may receive bolus infusions only after subjects in the preceding cohort have completed bolus infusions.

The DMC will meet no less than approximately every 6 months commensurate with enrollment.

The PK variables are the plasma concentrations of BRV (parent compound only) before, during, and after the first and 1 subsequent administration of iv BRV.

The primary safety variables are adverse events (AEs) and withdrawals due to AEs. Other safety variables are clinical laboratory parameters (hematology, chemistry, and endocrinology), and urinalysis. Clinically significant new or worsened abnormalities discovered during physical and neurological examinations will be recorded as AEs. Other safety variables also include 12-lead electrocardiogram (ECG), and vital signs (blood pressure [BP], pulse rate, respiratory rate [RR],

and temperature), all of which will be assessed with increased frequency during the iv PK Period.

The maximum study duration for an individual subject will be 68 days. Approximately 60 sites in Europe and North America are planned for participation in EP0065.

2 INTRODUCTION

Brivaracetam ((2S)-2-[(4R)-2-oxo-4-propyltetrahydro-1H-pyrrol-1-yl]butanamide) displays a high and selective affinity for the synaptic vesicle protein 2A (SV2A) in the brain. Binding to SV2A is believed to be the primary mechanism for BRV anticonvulsant activity. In 2016, marketing authorization for the use of oral and iv BRV as adjunctive treatment of partial-onset seizures (POS) in patients was granted in the EU, US, and Australia for patients 16 years of age and older with epilepsy and in Canada for patients 18 years of age and older with epilepsy.

Epilepsy affects all races of both sexes at any age from the first hour of life to extreme old age. The prevalence of epilepsy is 1% to 2% of the population and 4% of pediatric population in those developed countries where they have been studied; this is probably double in resource-poor countries (Banerjee and Hauser, 2008). In the US, the overall incidence of epilepsy ranges from 35.5 to 48 per 100,000 person-years and the prevalence ranges from 4.7 to 6.8 per 1000 population (Theodore et al, 2006). The incidence of new-onset epilepsy in the pediatric population is 44.5 per 100,000 persons per year (Wirrell et al, 2011). Within the pediatric population, the incidence is highest in children <5 years of age (approximately 60 to 100 per 100,000 person-years), decreasing to approximately 25 to 45 per 100,000 person-years in adolescents and young adults (Wirrell et al, 2011; Hauser et al, 1993).

In the US, 57% of newly diagnosed patients were classified as having POS (Zarrelli et al, 1999; Hauser et al, 1993). In the general population, the incidence of pediatric patients with epilepsy with POS is approximately 16 to 80 per 100,000 (Wirrell, et al, 2011; Banerjee and Hauser, 2008; Hauser et al, 1993).

The existing treatment options for POS in the pediatric population generally follow the treatment options for adults with the same disorder; clinical experience demonstrates that children may have results comparable to adults with administration of the conventional antiepileptic drugs (AEDs). More than 25% of pediatric patients have inadequate seizure control on currently available AEDs or experience significant adverse drug effects (Hadjiloizou and Bourgeois, 2007). There remains a need for potent AEDs with a positive benefit-risk profile in this population.

To date, oral formulations of BRV have been studied in the ongoing BRV pediatric development program as follows:

N01263 is a completed open-label, multicenter, fixed 3-step up-titration, adjunctive therapy study of the PK, safety, and efficacy of BRV in 100 subjects ≥ 1 month to <16 years of age with epilepsy. Doses of BRV (oral solution) were adjusted by body weight and did not exceed a maximum of 50mg/day, 100mg/day, and 200mg/day for each titration step. A total of 100 subjects enrolled in N01263: 99 subjects received study drug and were included in the Safety Set. Results from N01263 indicate that BRV was generally well tolerated and that the safety profile in pediatric subjects was consistent with the known safety profile in adult

subjects. In general, there were no clinically meaningful changes in laboratory parameters, vital signs, or ECG parameters. Trough plasma BRV concentrations increased proportionally to the dose.

N01266 is an ongoing open-label, multicenter study to evaluate the long-term safety and efficacy of bid administration of BRV oral solution and oral tablets in pediatric subjects with epilepsy who are receiving ≥ 1 AED other than BRV; the maximum allowable BRV dose is 5mg/kg/day not to exceed 200mg/day in subjects with body weights >40 kg. N01266 was initially designed as a long-term follow-up to N01263, which enrolled only subjects with either focal epilepsy or generalized epilepsy but was amended to also allow direct enrollment of subjects 4 years to <17 years of age who have focal epilepsy. Over 200 subjects have enrolled in N01266.

In addition to oral formulations, iv formulations of AEDs are particularly helpful as short-term replacements when use of oral formulations is not possible or feasible (eg, pre and postoperative patients, patients with acute gastrointestinal disorders, patients with acute swallowing disorders). Brivaracetam injection has been approved for use as adjunctive therapy in the treatment of POS in patients 16 years of age and older with epilepsy and may be used when oral administration of BRV is temporarily not feasible. Treatment with BRV may be initiated with tablets, oral solution, or solution for injection.

The current study, EP0065, is planned to evaluate the PK, safety, and tolerability of iv BRV administered as a 15-minute infusion and bolus (up to 2-minute infusion) in subjects ≥ 1 month to <16 years of age with epilepsy.

The iv dose for subjects initiating BRV in this study was predicted in N01331, which modeled based on PK data from N01263 and N01256 (BRV adult study) and simulated the BRV iv concentrations in pediatric subjects. Based on the results of N01331, in the pediatric population 1 month to <17 years of age, an iv injection 15-minute infusion or bolus (up to 2-minute infusion) of 4mg/kg/day (2mg/kg bid) regimen (with a maximum of 200mg/day [100mg bid] for subjects with body weights ≥ 50 kg) results in plasma concentrations in the same range as seen in adults receiving 200mg/day (100mg bid), the maximum recommended dose in adults with POS. These data support using a mg-to-mg equivalent to the oral dose for OLB and RxB subjects. As demonstrated in the concentration-effect analysis CL0258 using levetiracetam PK and pharmacodynamic (PD) data from adults and children and BRV PK and PD data in adults (N01358) and PK data in children (N01263), in subjects 4 to 16 years of age, similar weight-normalized doses are needed to achieve the same efficacy as compared with adults, with a maximum response at 4mg/kg/day.

More detailed information regarding the nonclinical and clinical development programs for BRV is provided in the Investigator's Brochure.

3 STUDY OBJECTIVES

The primary objective is to evaluate the PK, safety, and tolerability of BRV administered as a 15-minute iv infusion and iv bolus (up to 2-minute infusion) in subjects ≥ 1 month to <16 years of age with epilepsy.

4 STUDY VARIABLES

4.1 Pharmacokinetic variables

- Plasma concentration of BRV (parent compound only) before, during, and after iv BRV administration

4.2 Safety variables

4.2.1 Primary safety variables

- Adverse events throughout the study
- Subject withdrawals due to AEs

4.2.2 Other safety variables

- 12-lead ECG values before, during, and after each iv BRV administration
- BP, pulse rate, RR, and temperature values before, during, and after each iv BRV administration
- Clinical laboratory parameters (hematology, chemistry, and endocrinology) pre and posttreatment
- Urinalysis parameters pre and posttreatment

5 STUDY DESIGN

5.1 Study description

EP0065 is a Phase 2 multicenter, open-label study to evaluate the PK, safety, and tolerability of iv BRV administered as a 15-minute iv infusion and an iv bolus (up to 2-minute infusion) in subjects ≥ 1 month to < 16 years of age with epilepsy.

It is planned for approximately 50 enrolled subjects to receive iv BRV in the following age-based cohorts (approximately 12 subjects/cohort):

- Cohort 1: ≥ 12 to < 16 years
- Cohort 2: ≥ 6 years to < 12 years
- Cohort 3: ≥ 2 to < 6 years
- Cohort 4: 1 month to < 2 years

The following subjects will be eligible for enrollment in EP0065:

- QLB subjects: currently receiving oral BRV as participants in a long-term, open-label study
- RxB subjects: currently receiving prescribed oral BRV from commercial supply
- IOB subjects: not currently receiving BRV; first dose of BRV in EP0065 will be oral tablet or solution
- IIB subjects: not currently receiving BRV; first dose of BRV in EP0065 will be by iv infusion

For OLB and RxB subjects, the maximum BRV dose is 5mg/kg/day (rounded). For IOB and IIB subjects, the maximum BRV dose is 4mg/kg/day. **Throughout the study, no subject may receive a dose greater than BRV 200mg/day.** Subjects will receive oral BRV (tablets or oral solution) in equally divided doses; BRV oral solution may be given by enteric administration (eg, by feeding tube) based on subject need.

The EP0065 study periods and visits are described below. The PK assessments will be made during the iv PK Period only and safety data will be collected throughout the study, with intensive collection of safety data with each iv BRV dose administered. A Schedule of Study Assessments is provided for the Screening through iv PK Periods in [Table 5-1](#) and for the Down-Titration Period and Safety (BRV-free) Periods (for subjects not continuing BRV) in [Table 5-4](#).

Screening Period (1 to 10 days)

During the Screening Period, the OLB and RxB subjects will continue treatment with oral BRV using their assigned open-label study supply or prescribed commercial supply, respectively. The IOB and IIB subjects will not receive BRV during this period.

The OLB subjects will temporarily discontinue assessments in their long-term, open-label study when they enter EP0065. As such, all assessments for these subjects during the Screening Period (and subsequent periods of EP0065) will be recorded in the EP0065 Case Report form (CRF) until they return to a long-term, open-label study or discontinue BRV treatment.

IOB Treatment Period (2 to 10 days of oral BRV treatment; for IOB subjects only)

Only IOB subjects who meet all eligibility criteria may participate in the IOB Treatment Period. No other subjects may participate in this period.

During the IOB Treatment Period, IOB subjects will initiate treatment with oral BRV 2mg/kg/day not to exceed 100mg/day for subjects with body weights ≥ 50 kg and must have, at minimum, 2 days of treatment with oral BRV before entry into the iv PK Period. Subjects who do not enter the iv PK Period will not be eligible for the long-term, open-label study.

The Investigator is permitted to adjust the oral BRV dose during the IOB Treatment Period in accordance with medical judgment (with a maximum dose of 4mg/kg/day, not to exceed 200mg/day for subjects with body weights ≥ 50 kg); however, subjects must have no change in the oral BRV dose for the 2 days prior to entry into the iv PK Period.

iv PK Period (1 to 6 days, with Day 1 defined as the initial day of iv BRV infusion)

[figure not shown]
During the iv PK Period, iv BRV will be administered every 12 hours ± 2 hours (q12h ± 2 h). All subjects are to receive 1 to 2 consecutive doses of BRV; however, based on medical need, subjects may receive up to 10 consecutive doses of iv BRV. The PK sampling will occur with the first iv BRV administration and with 1 other iv BRV administration.

The first dose of iv BRV will be as follows:

- OLB, RxB, and IOB subjects: mg-to-mg equivalent of the oral BRV dose immediately prior to the iv PK Period; administered q12h ± 2 h after prior oral dose
- IIB subjects: 1mg/kg not to exceed a maximum of 50mg for subjects ≥ 50 kg

After subjects have completed PK sampling with 2 iv BRV infusions, the Investigator may adjust the BRV dose, but the adjusted dose must not exceed 5mg/kg/day (rounded) for OLB and RxB subjects and 4mg/kg/day for IOB and IIB subjects (with the maximums not to exceed 200mg/day). During the iv PK Period, BRV may only be administered intravenously. Enrollment will be sequential by descending age beginning with Cohort 1. For each cohort, the first half will receive the 15-minute infusion. The Data Monitoring Committee (DMC) will then meet to review safety and, as available, PK data (Figure 5–1). After the DMC safety review, the remaining half in that cohort will receive iv BRV as a bolus (up to 2-minute infusion) and the next cohort may begin the 15-minute infusion. Subjects may receive bolus infusions only after subjects in the preceding cohort have completed bolus infusions and the DMC have reviewed these data. The DMC will meet no less than approximately every 6 months commensurate with enrollment.

Figure 5–1: Schematic of sequential cohort enrollment during the iv PK Period

DMC=Data Monitoring Committee; inf=infusion; iv=intravenous; PK=pharmacokinetic

Telephone Contact (TC)-1 will occur 1 to 3 days after completing the final iv BRV dose in the iv PK Period to facilitate reporting of infusion-site related AEs.

The schedules for PK sampling, 12-lead ECGs, and vital sign assessments during the iv PK Period are provided in Table 5–2 (15-minute infusion), and Table 5–3 (bolus [up to 2-minute infusion]).

Down-Titration Period (up to 4 weeks) and Safety (BRV-free) Period (2 weeks)

Subjects who receive ≥4 doses of BRV during either the IOB Treatment Period or the iv PK Period and who do not plan to continue treatment with BRV or who discontinue from the study will enter a Down-Titration Period. Subjects who have received <4 doses of BRV may have BRV down titrated at the discretion of the Investigator. During the Down-Titration Period, subjects will have their BRV dose reduced by a maximum of half the dose every week for a maximum of 4 weeks until a dose of 1mg/kg/day (50mg/day for subjects with body weights ≥50kg) is reached. Subjects not able to receive oral BRV for down titration, may receive iv BRV for down titration. In the latter circumstance, the subjects may receive more than 10 consecutive

doses of iv BRV in accordance with the Investigator's discretion. A 2-week Safety (BRV-free) Period will follow the final dose of BRV.

Safety assessments will be collected throughout this period (Table 5-4).

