6 SELECTION AND WITHDRAWAL OF SUBJECTS

6.1 Inclusion criteria

To be eligible to participate in this study, all of the following criteria must be met:

1. Subject or the parent(s) or legal representative of the subject has signed and dated an Institutional Review Board (IRB)/Independent Ethics Committee (IEC) approved written ICF. The ICF or a specific Assent form, where required, will be signed and dated by minors.
2. The Investigator considers the subject/legal representative to be reliable and able to comply with all study requirements.
3. Subject is male or female from ≥ 1 month to <16 years of age. For subjects who are <1 year from birth and who were preterm infants, the corrected gestational age should be used for this entry requirement. The corrected gestational age is calculated by subtracting the number of weeks born before 37 weeks of gestation from the chronological age.
4. Subject weighs ≥ 3 kg (6.6lbs).
5. Subject has a diagnosis of epilepsy.
6. Subject is an acceptable candidate for venipuncture and iv infusion.
7. Subject being treated with ≥ 1 AED (including BRV) without a change of dose regimen for at least 7 days prior to Screening.
8. Subject is not being treated with vagus nerve stimulation (VNS), OR the subject is being treated with VNS and the settings have been constant for ≥ 7 days prior to Screening.
9. For female subjects, the subject is
 - Not of childbearing potential
 - OR-
 - Of childbearing potential, and
 - Is not sexually active
 - Has a negative pregnancy test
 - OR-
 - Of childbearing potential, and
 - Is sexually active
 - Has a negative pregnancy test

- Understands the consequences and potential risks of inadequately protected sexual activity, understands and properly uses contraceptive methods, and is willing to inform the Investigator of any contraception changes. Medically acceptable contraceptive methods for the study include, but are not limited to:
 - Oral or depot contraceptive treatment with at least ethinylestradiol 30µg per intake or ethinylestradiol 50µg per intake if also taking one of the following: carbamazepine, phenobarbital, primidone, phenytoin, oxcarbazepine, St. John's Wort, or rifampicin.
 - Barrier contraception: Intra Uterine Device, diaphragm with spermicide, male or female condom with spermicide
 - Abstinence from sexual intercourse

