7.2.2 Down-Titration Period

All subjects who have received ≥ 4 doses of BRV during either the IOB Treatment Period or the iv PK Period and who will not continue BRV will have their BRV dose reduced by a maximum of half the dose every week for a maximum of 4 weeks until a dose of 1mg/kg/day (50mg for subjects with body weights ≥ 50 kg) is reached. Subjects who have received < 4 doses of BRV may have BRV down titrated at the discretion of the Investigator. Subjects not able to receive oral BRV for down titration, may receive iv BRV for down titration. In the later circumstance, the subjects may receive more than 10 consecutive doses of iv BRV in accordance with the Investigator's discretion.

The OLB subjects who discontinue BRV during the Screening Period will return to the long-term, open-label study for down titration of BRV.

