8.5 TC-2

Telephone Contact-2 is only applicable to subjects who participate in the Down-Titration Period for more than 2 weeks; TC-2 should be conducted approximately half way through the Down-Titration Period.

- Concomitant medications including AEDs
- AEs
- Withdrawal criteria

8.6 Visit 13

This visit is applicable only to subjects who have participated in the Down-Titration Period or to subjects who need to withdraw from the study and do not need to have BRV down titrated.

- Concomitant medications including AEDs
- Physical examination (brief)
- Neurological examination (brief)
- Body height
- Vital signs (BP, pulse rate, RR, and temperature)
- 12-lead ECG
- Clinical chemistry, hematology, and endocrinology
- Urinalysis for subjects for whom urine sample collection is feasible
- Pregnancy testing for females of childbearing potential (urine test)
- AEs
- C-SSRS (for subjects ≥ 6 years of age); version per [Section 10.3.3](#)
- Collect oral BRV

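### The 4-dose rule for mandatory Down-Titration leaves out oral BRV taken before the iv PK Period by OLB and RxB subjects, and the Summary words the rule differently

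*Protocol*

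**What the plan says.** **The taper rule.** Protocol 5.1 requires Down-Titration for subjects with at least 4 "doses of BRV during either the IOB Treatment Period or the iv PK Period and who do not plan to continue treatment with BRV". Protocol 7.2.2 applies it to subjects with at least 4 "doses of BRV during either the IOB Treatment Period or the iv PK Period and who will not continue BRV", and SAP 2.3 repeats the 5.1 wording. The Summary instead refers to subjects with at least 4 "doses of BRV and do not plan to continue treatment with BRV after completion of the iv PK Period" and names no period. For subjects below the threshold, 5.1 says that those with fewer than 4 "doses of BRV may have BRV down titrated at the discretion of the Investigator"; that sentence names no period either.

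**Who accrues counted doses.** The IOB Treatment Period is reserved for IOB subjects, who "must have, at minimum, 2 days of treatment with oral BRV before entry into the iv PK Period". OLB and RxB subjects take their own oral BRV through Screening and go straight to the iv PK Period, where the planned course is 1 to 2 iv doses (up to 10 on medical need).

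**Established users elsewhere.** Protocol 7.2.2 adds: "The OLB subjects who discontinue BRV during the Screening Period will return to the long-term, open-label study for down titration of BRV". There is no corresponding sentence for OLB or RxB subjects who stop after iv dosing.

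**Follow-up after stopping.** Protocol 8.6, on Visit 13, sets this limit: "This visit is applicable only to subjects who have participated in the Down-Titration Period or to subjects who need to withdraw from the study". The withdrawing group meant there is those who require no taper. TC-3 depends on Visit 13 (8.7; Table 5-4, footnote b). Protocol 5.1, 5.2 and the title of Table 5-4, however, apply that schedule to subjects who do not continue BRV or do not enter the long-term study.

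**The concern.** The threshold implies that 4 doses, or 2 days of bid treatment, are enough exposure to call for gradual withdrawal. The operative sections then count exposure in a way that misses the children who have had the most of it. A child on maintenance BRV who stops after the planned iv doses falls below the threshold, while a child who started oral BRV two days earlier is above it. The documents give no reason for the difference.

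Two sites could also treat the same child differently, depending on whether they follow the Summary or 5.1 and 7.2.2. The sentence for fewer than 4 doses does not settle it: a long-term user has not literally received fewer than 4 doses of BRV, so such a subject fits it only if the period limit is read across from the sentence before.

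The Visit 13 question is separate. It arises for any group, including IIB subjects with fewer than 4 doses. At stake are the posttreatment laboratory, urinalysis and ECG assessments and a planned contact about 2 weeks after the last dose.

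**Working it through.** The plan gives no sample-size or power figure that bears on this point. The check is a dose count by group and a comparison of sections.

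**1. The plan's own durations (Protocol 5.1.1).** Total: 10 (Screening) + 10 (IOB) + 6 (iv PK) + 28 (taper) + 14 (BRV-free) = 68 days, as stated. BRV administration: 10 (IOB) + 6 + 28 = 44 days, as stated.

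**2. Doses counted under 5.1, 7.2.2 and SAP 2.3.** Oral dosing is bid.

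| Subject stopping BRV | Counted doses | Mandatory taper? |
|---|---|---|
| IOB, minimum oral treatment | 2 days × 2 = 4, before any iv dose | Yes |
| OLB or RxB, 1 to 3 iv doses | 1 to 3 | No |
| IIB, 1 to 3 iv doses | 1 to 3 | No |

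**3. Doses OLB and RxB subjects have actually taken.** With d Screening days (1 to 10) and k iv doses (1 to 3), in-study doses = 2d + k.
- Minimum: 2 × 1 + 1 = 3. Maximum: 2 × 10 + 3 = 23.
- Only d = 1 with k = 1 gives fewer than 4. The next smallest totals are 2 + 2 = 4 and 4 + 1 = 5.
- Inclusion criterion 7 asks for at least one "AED (including BRV) without a change of dose regimen for at least 7 days prior to Screening". Assuming that the stable drug was bid BRV, this adds 7 × 2 = 14 doses, giving 14 + 3 = 17 to 14 + 23 = 37.

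**4. Dose at stopping, relative to the dose at which the protocol ends a taper.**
- OLB/RxB at the maximum: 5 ÷ 1 = 5 times. At 50 kg or more: 200 ÷ 50 = 4 times.
- IOB: 2 ÷ 1 = 2 times at the starting dose, 4 ÷ 1 = 4 times at the maximum.

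**5. Last planned contact for an untapered completer who stops BRV.**
- On 8.6: TC-1, 1 to 3 days after the final iv dose.
- On 5.1, 5.2 and the Table 5-4 title: TC-3, about 14 days after the final dose.
- Difference: 14 − 3 = 11 to 14 − 1 = 13 days.

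**6. After the change.**
- OLB/RxB: at least 17 doses under the assumption in step 3, so taper is mandatory. IOB: at least 4, unchanged. IIB with 1 to 3 doses: still discretionary.
- A taper from 5 mg/kg/day, at most halving each week, goes 5 → 2.5 → 1.25 → 1: 3 steps, within 4 weeks.
- OLB/RxB BRV time in the study: at most 10 + 6 + 28 = 44 days, equal to the stated maximum. Duration: at most 10 + 6 + 28 + 14 = 58 days, inside 68.

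**The case against.** The strongest reply is that nothing here tells anyone to stop BRV abruptly. If the sentence on fewer than 4 doses applies, the Investigator may taper; if neither sentence applies, nothing forbids it. This stands: what is missing is a mandate. It does not explain why a child with 4 oral doses is not left to the same discretion.

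The Summary may also be a shortened form of the rule in 5.1. A reader might infer that it plainly makes the taper mandatory for every established user. It does not go that far: it does not say that pre-study doses count, and in-study doses alone can total 3. The proposed count therefore makes explicit something that no section now states.

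The affected group is narrow. Subjects who continue oral BRV are expected to enter a long-term study, and 8.3 provides for all four groups to do so. The 5-fold dose ratio is a worst case for lighter children; at 50 kg or more the ceiling is the same for every group.

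A reader might further infer that untapered subjects in general lose their posttreatment assessments. The text does not support that: 6.3 and 8.6 both give Visit 13, and hence TC-3, to subjects who withdraw without a taper. Nor does the sentence on OLB subjects stopping in Screening show that a parallel RxB rule is missing. At that stage RxB subjects take prescribed commercial BRV and have received no study dose.

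**Conclusion.** The inconsistency is real, and the operative wording protects longer-exposed children less than newly treated ones. An OLB or RxB subject who permanently stops after 1 to 3 iv doses has no mandatory taper, and discretion applies at best by reading a period limit into a sentence that has none. The in-study dose count assumes bid dosing; the totals of 17 to 37 further assume that the 7 stable days were on BRV.

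On follow-up, only the subject who completes the iv PK Period, stops BRV and is not tapered is unsettled. The possible loss is Visit 13 data and active detection of new non-serious AEs. SAEs are still reported to 30 days (10.1.2.3), and ongoing AEs are usually followed for 30 days after IMP (10.1.3).

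A reader might take this as an analysis problem. No analysis set, primary summary or sample-size figure depends on it, and SAP 3.2.5 assigns periods by whether a subject actually down-titrated. The documents do not give the number of subjects affected; it is probably small. Severity: minor.

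**What to change.** 1. In the Summary, Protocol 5.1, 7.2.2 and SAP 2.3, state that the 4-dose threshold counts all consecutive BRV doses, including oral BRV taken before and during Screening. Use the same count in the mandatory sentence and in the sentence for fewer than 4 doses. Except cases of immediate discontinuation: PDILI under 6.3.1, pregnancy under 10.1.4, or another safety reason.
2. Reword 8.6 so that Visit 13, and with it TC-3, also applies to subjects who complete the iv PK Period, do not continue BRV and are not tapered.
3. Align SAP 2.2.2.2, which now ties posttreatment parameters to subjects who down-titrate, so that it refers to all subjects with Visit 13.

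No taper provision is needed for RxB subjects who stop in Screening, and SAP 3.2.5 can stay as it is.

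The cost is one wording amendment with matching SAP text and no extra patients. Each affected subject has at most a 28-day taper, one visit with a blood draw, and one or two calls, all within the stated 44-day and 68-day maxima.
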